15.1.1.2 PERCENT REDUCTION OF INFUSION DURATION FROM PRE-STUDY AVERAGE OF RECENT 3 INFUSIONS

Percent reduction is with respect to the shortest tolerated infusion for the participant.

The pre-study infusion duration is derived as the average of the duration of 3 most recent

Document: \\ieedc-

 $vnasc01\\BIOS data\\Sanofi\\Fabrazyme\\IAB16602\\Biostatistics\\Documentation\\SAP\\SAP\\Sanofi\\Finally and the properties of t$

Version\lps17726-16-1-9-sap.docx

Author: Version Number: Final V1.0

Version Date: 22Oct2024

Template No.: CS_TP_BS016 Revision 7 Reference: CS_WI_BS005

Effective Date: 01Nov2021

PROTOCOL LPS17726

Analysis Plan Template

Page 44 of 65

infusions the participant received prior to participating to this study. Data for pre-study infusion durations are captured on the Pre-Study Fabrazyme Treatment eCRF page.

15.1.2 DERIVATIONS

- Infusion Interruption Duration (minutes) = (Interruption Stop Time Interruption Start Time)
- Actual infusion duration (minutes) = (Infusion Stop Time Infusion Start Time) –
 Infusion Interruption Duration (minutes)
- Average of pre-study infusion duration (minutes) = sum of all pre-study infusion duration (minutes) / number of pre-study infusions
- Percentage reduction of infusion duration (%) =100*[(Average of pre-study infusion duration (minutes) Actual shortest infusion duration tolerated (minutes)] /Average of pre-study infusion duration (minutes)
- Percentage change of infusion duration (%) =100*[Actual shortest infusion duration tolerated (minutes) Average of pre-study infusion duration (minutes)] /Average of pre-study infusion duration (minutes)

15.1.3 INTERCURRENT EVENT HANDLING AND DATA IMPUTATION FOR PRIMARY ENDPOINT VARIABLE(S)

Refer to Sections 7.2 and 7.3.1.1 for details about intercurrent events and management of missing data.

15.1.4 ANALYSIS OF PRIMARY ENDPOINT VARIABLE(S)

Primary endpoints will be summarized descriptively for cohorts 1-4 pooled for the ITT analysis set. Details of the descriptive statistics is described in Section 7: 'Statistical Considerations'. A

Document: \\ieedc-

Author:

vnasc01\BIOSdata\Sanofi\Fabrazyme\IAB16602\Biostatistics\Documentation\SAP\SAP\Sanofi\Final

Version\lps17726-16-1-9-sap.docx

Version Number: Final V1.0

Version Date: 22Oct2024

Template No.: CS_TP_BS016 Revision 7 Reference: CS_WI_BS005

Effective Date: 01Nov2021

PROTOCOL LPS17726

Analysis Plan Template

Page 45 of 65

Final V1.0

corresponding listing presenting the primary endpoint values will also be provided per cohort for the ITT analysis set.

Each participant's shortest tolerated infusion duration and individual % change in infusion duration will be presented graphically in separate waterfall plots for the ITT analysis set.

For analysis of the primary endpoints IARs will be considered separate only when they are occurring in separate infusions. IARs occurring at multiple time points during a single infusion will be considered as a single IAR.

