4.0 STUDY DESIGN

4.1 Overall Design

This is a Phase 4, prospective, open label, single arm, interventional study, to be conducted in the US, to evaluate the safety and tolerability of Fabrazyme at approved dose of 1 mg/kg with increases in the infusion rate and reduced infusion volume.

Up to 14 participants with FD will be enrolled to receive study intervention in 4 cohorts:

- Cohort 1: 3 Fabrazyme experienced female participants (body weight \geq 30 kg).
- Cohort 2: 3 Fabrazyme experienced non-classic male participants (body weight ≥30 kg).
- Cohort 3: 4 Fabrazyme experienced classic male participants (body weight ≥30 kg).
- Cohort 4: 4 Fabrazyme experienced participants (body weight <30 kg).

Classic FD is defined by α GAL level in dried blood spot or leukocyte below 3% of normal value and all others are considered as non-classic disease.

The study schema is presented in Section 1.2. Screening will be performed up to 4 weeks prior to the first dose of study intervention. All 4 cohorts of this study will be enrolled simultaneously. Enrolled participants will receive treatment for up to 16 weeks (up to 9 infusions) and have an End-of-Study Visit 28 weeks after the start of the treatment. Participants will undergo visits and study procedures as shown in Schedule of Activities (SoA) presented in Section 1.3.

All participants will receive Fabrazyme infusions at dose of 1 mg/kg at the study site. The participants are not required to stay at the site after completion of the infusion, unless the Investigator considers it medically necessary. The infusion duration will shorten, and the infusion rate will rise with each successfully tolerated infusion (ie, an infusion completed within a duration not exceeding 120% of planned duration, without infusion associated reaction [IAR]), until reaches the minimum infusion duration of 20 minutes for participants in cohorts 1 to 3 (≥30 kg) and 30 minutes for participants in cohort 4 (<30 kg). Guidance for increasing the rate of infusion (and consequently decreasing the infusion duration) are presented in Section 6.2. When the participant successfully reaches the shortest infusion duration planned for the cohort which he/she belongs, he/she will be considered a treatment completer and will not receive any further infusion as part of the study, regardless of whether the treatment period reaches 16 weeks or not.

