9.3.2 Primary Endpoint Analysis

Table 5 Primary Endpoint Analysis

Endpoint	Statistical Analysis Methods
% Reduction of infusion duration from prestudy average of recent 3 infusions in participants with confirmed diagnosis of FD, age 2 to 65 years, Fabrazyme-experienced, treated for at least 3 months without IARs during recent 3 infusions.	The primary endpoint will be analyzed using descriptive statistic, focusing on median and quantiles of % reduction of infusion duration from prestudy average of recent 3 infusions (pooled all cohorts).
Shortest infusion duration tolerated by each participant in participants with confirmed diagnosis of FD, age 2 to 65 years, Fabrazyme-experienced, treated for at least 3 months without IARs during recent 3 infusions.	The primary endpoint will be analyzed using descriptive statistic, focusing on median and quantiles of the shortest infusion duration tolerated by each participant (pooled all cohorts).

Abbreviations: FD = Fabry disease; IAR = infusion associated reaction.

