1.1 Synopsis 3.0 Objectives, Endpoints and Estimands	The second primary estimands involving the enzyme replacement therapy (ERT)-naïve population was deleted. The population attribute of all secondary estimands were adjusted to remove the mention on ERT-naïve population. The intercurrent event attribute for all endpoints was adjusted to add "A treatment policy approach will be applied in case pre-medications are not given as described within the protocol. No action will be taken for this event for the analysis even when pre-medications are not given as described within the protocol."	Cohort 5, previously composed of ERT-naïve participants, was removed from the study as a way to mitigate with participant enrollment delay. ERT-naïve patients are considered to have the highest risk of not tolerating shorter infusions. This cohort is removed to minimize increase of risk related to making enrollment of cohorts 2-4 parallel. Changes in intercurrent event attribute was made to explicitly add full clarity on management of endpoints in case pre-medications are not given as described within the protocol.
1.1 Synopsis 4.1 Overall Design	The description and flow of the staged enrollment was removed (together with Figure 2) and the following sentence was added "All 4 cohorts of this study will be enrolled simultaneously."	Initial data shows that infusion duration shortening is very well tolerated and participants can reach 20-minute duration without experiencing a single infusion associated reaction (IAR). Considering this, and that cohort 5 (treatment-naïve patients, which has the highest risk of not tolerating shorter infusions) was removed from the study, the risk for the remaining cohorts (2, 3, and 4) not tolerating these shorter infusions is relatively low. Therefore, the study will proceed to enroll all cohorts simultaneously.
1.1 Synopsis 4.1 Overall Design	The number of participants was reduced from 18 to 14, and cohort 5 description was deleted.	Cohort 5, previously composed of ERT-naïve participants, was removed from the study as a way to mitigate with participant enrollment delay. ERT-naïve patients are considered to have the highest risk of not tolerating shorter infusions. This cohort is removed to minimize increase of risk related to making enrollment of cohorts 2 to 4 parallel.

Section # and Name	Description of Change	Brief Rationale

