3 STUDY DESIGN

3.1 GENERAL DESCRIPTION

This is a Phase 4, prospective, open label, single arm, interventional study, to be conducted in the US, to evaluate the safety and tolerability of Fabrazyme at approved dose of 1 mg/kg and increased infusion rate and reduced infusion volume.

Up to 14 participants with Fabry disease will be enrolled to study intervention in 4 cohorts:

- Cohort 1: 3 Fabrazyme experienced female participants (body weight ≥30 kg)
- Cohort 2: 3 Fabrazyme experienced non-classic male participants (body weight ≥30 kg)
- Cohort 3: 4 Fabrazyme experienced classic male participants (body weight ≥30 kg)
- Cohort 4: 4 Fabrazyme experienced participants (body weight <30 kg)

Classic FD is defined by α GAL level in dried blood spot or leukocyte below 3% of normal value and all others are considered as non-classic disease.

Screening will be performed up to 4 weeks prior to the first dose of study intervention. Enrolled participants will receive treatment for up to 16 weeks and have an End-of-Study Visit 28 weeks after the start of the treatment. Participants will undergo visits and study procedures as shown in Schedule of Activities (SoA) presented in Section 1.3 of the protocol. A flow chat illustrating the key components of the study is provided in Figure 1.

Document: \\ieedc-

 $vnasc01\BIOS data\Sanofi\Fabrazyme\IAB16602\Biostatistics\Documentation\SAP\SAP\Sanofi\Final$

Version\lps17726-16-1-9-sap.docx

Author: Version Number: Final V1.0

Version Date: 22Oct2024

[figure not shown]
Template No.: CS_TP_BS016 Revision 7 Reference: CS_WI_BS005

Effective Date: 01Nov2021

Page 18 of 65

Figure 1: Study Schema

Abbreviations: ADA = anti-drug antibody (ie, anti-agalsidase beta IgG antibody); AE = adverse event; AESI = adverse event of special interest; EOS = end-of-study; EOT = end-of-treatment; IAR = infusion associated reaction; lyso-GL3 = globotriaosylsphingosine; Q2W = every 2 weeks; SAE = serious adverse events; V = visit; W = week.

- a. V1 and V2 can take place on the same day. The number of visits during the Study Intervention Period (ie, Visits 2 to 10) may differ between participants, as those having a second IARs will discontinue the study intervention, and those who successfully reaches the shortest infusion duration planned for the cohort to which they belong will be considered as treatment completers. All participants will stay in the study for the follow-up visits at Week 12 and Week 28.

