3.3 CHANGES TO ANALYSIS FROM PROTOCOL

The following presents the updated changes to analysis from protocol section 9.0, version 2.0 (Protocol Amendment Number 1.0), dated 20May2024.

Table B - Changes to Analysis from Protocol

Analysis in SAP	
Reason for Update: ADA analysis will include summaries of ADA attributes, titer, incidence, and kinetics of ADA response. Also, "6 months follow-up" will include "each visit where plasma lyso-GL3 (ng/mL)/ADA titer is recorded" to make it clear that all post-baseline visits will be considered for analysis as per the windowing convention described in Section 6.6 'Windowing Conventions'. Refer to Section 15.3.1 for the full descriptions of derivations and analyses.	
Reason for Update: Analyses with limited value are removed: The 95% confidence intervals will not be presented due to the small sample size. Shift tables will not be presented. Change from baseline will only be derived for continuous measurements of select variables specified in the SAP. See Section 7: 'Statistical Considerations'	

Document: \\ieedc-

vnasc01\BIOSdata\Sanofi\Fabrazyme\IAB16602\Biostatistics\Documentation\SAP\SAP\Sanofi\Final

[figure not shown]
Version\lps17726-16-1-9-sap.docx

Author: Version Number: Final V1.0

Version Date: 22Oct2024

Template No.: CS_TP_BS016 Revision 7 Reference: CS_WI_BS005

Effective Date: 01Nov2021

Page 23 of 65

Analysis in Protocol	Analysis in SAP
Categorical data will be summarized using count and percentage (the percentage of participants in each category relative to the total number of participants in the relevant analysis set or relative to the total number of participants in the relevant analysis set, with assessments available [where appropriate]) in each category. A 95% CI will be provided for the binary endpoint as appropriate. The change from baseline in distribution for the categorical endpoint_will be presented with a shift table; number and percentage of participants will be provided.	
Analysis of Cohorts ■ The data will be summarized per cohort and by pooled cohorts as described in Sections 9.3.2, 9.3.3 and 9.3.4, and where appropriate, per infusion duration.	Reason for Update: Data will be summarized by pooled cohorts 1-4 only. This is because there are very few participants within each cohort. See Section 7: 'Statistical Considerations'

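### Both primary endpoints are tabulated only for all cohorts pooled, so the median shortest duration stops reflecting the <30 kg cohort once 8 of the 10 heavier participants reach 20 minutes, and no primary summary statistic is given by weight group

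*SAP*

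**What the plan says.** Protocol 4.1 sets the shortest planned durations at "20 minutes for participants in cohorts 1 to 3 (≥30 kg) and 30 minutes for participants in cohort 4 (<30 kg"), and Protocol 6.2 gives each weight group its own flow chart for shortening the infusion. SAP 3.1 plans the numbers: "Up to 14 participants with Fabry disease will be enrolled to study intervention in 4 cohorts", made up of 3 women, 3 non-classic men and 4 classic men at or above 30 kg, and 4 participants below 30 kg.

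The estimand summary measure for both primary endpoints is the median and quantiles (Protocol Table 2, SAP Table A). Protocol Table 5 pools the analysis, for example "focusing on median and quantiles of the shortest infusion duration tolerated by each participant (pooled all cohorts"). SAP 15.1.4 does the same: "Primary endpoints will be summarized descriptively for cohorts 1-4 pooled". SAP Table B extends this to the data summaries generally: "Data will be summarized by pooled cohorts 1-4 only", because each cohort has very few participants. SAP 7.5 plans no subgroup analyses.

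SAP 15.1.4 refers to Section 7 for the statistics, so the table also carries n, mean, SD, minimum and maximum. SAP 15.1.4 adds a per-cohort listing of the primary values and a waterfall plot for each primary endpoint. SAP 15.2.3 adds a bar chart split by cohort and planned duration, and a per-cohort listing with responder flags.

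**The concern.** A median over a mixed group is informative about a subgroup only if that subgroup's values can fall near the middle of the ordering. Cohort 4's best planned result is 30 minutes, so its values rank behind every heavier participant who reaches 20, whether cohort 4 succeeds or fails. If the heavier participants do well, cohort 4's outcome no longer enters the median.

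The sponsor expects the heavier participants to do well. The rationale for Amendment 1.0 in Protocol 10.6 says that "participants can reach 20-minute duration without experiencing a single infusion associated reaction (IAR"), and attributes this to the first 4 participants in cohorts 1 and 2. For patients under 30 kg, the experience cited in Protocol 2.1 reaches 60 minutes. The statistic named in the estimand is therefore least responsive in the group where the documents cite the least experience with short infusions. The study aims to give guidance on how far the rate can be raised, and each weight group has its own schedule.

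**Working it through.** **Inputs from the documents.** Cohort sizes 3 + 3 + 4 + 4 = 14, which reproduces the planned maximum (SAP 3.1). Targets are 20 minutes (n = 10) and 30 minutes (n = 4). A participant who tolerates nothing gets 0% reduction (Protocol Table 2) and, in SAP 7.3.1.1.2, a duration equal to their own pre-study mean. Percent reduction = 100 × (pre-study mean − shortest tolerated) / pre-study mean (SAP 15.1.2).

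**Assumptions.** The documents give no pre-study durations. I use 120 minutes for illustration and 90-240 minutes as a range. Actual durations are taken as equal to planned.

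**Order statistics for n = 14.** The median is the mean of the 7th and 8th values. With the SAS default definition, Q1 is the 4th value and Q3 the 11th.

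**1. Shortest duration.** Cohorts 1-3 are at 20 minutes except where a row states otherwise, and a failure is set to 120:

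| Scenario | Q1 | Median | Q3 | Max | Mean |
|---|---|---|---|---|---|
| Cohort 4 all succeed | 20 | 20 | 30 | 30 | 22.9 |
| 1 of cohort 4 fails | 20 | 20 | 30 | 120 | 29.3 |
| 3 of cohort 4 fail | 20 | 20 | 30 | 120 | 42.1 |
| All 4 of cohort 4 fail | 20 | 20 | 120 | 120 | 48.6 |
| 1 of cohort 1 fails, cohort 4 succeeds | 20 | 20 | 30 | 120 | 30.0 |
| All 3 of cohort 1 fail, cohort 4 succeeds | 20 | 25 | 30 | 120 | 44.3 |
| All 4 of cohort 3 fail, cohort 4 succeeds | 20 | 30 | 120 | 120 | 51.4 |

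The median stays at 20 after total cohort 4 failure for failure values of 90, 120, 180 or 240 minutes. If cohorts 1-3 all take 24 minutes (120% of 20), it stays at 24. It moves when a whole heavier cohort fails, even one of 3. The second and fifth rows show the attribution problem: one failure in either weight group gives the same quartiles and maximum, and means of 29.3 and 30.0.

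**2. When the condition is met.** At least 8 of the 10 heavier participants must tolerate 20 minutes. If each does so independently with probability 0.7 / 0.8 / 0.9 / 0.95, the binomial probability of this is 38% / 68% / 93% / 99%.

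**3. Percent reduction, common pre-study mean of 120.** Heavier participants at target: 100 × (120 − 20)/120 = 83.3%. Cohort 4 at target: 100 × (120 − 30)/120 = 75.0%. The pooled median is 83.3% whether all four of cohort 4 succeed or all four fail. Q1 stays at 75.0% with one, two or three failures and falls to 0% with four. The mean falls from 81.0% to 59.5% with four.

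**4. Percent reduction, differing pre-study means.** The median can now move. A cohort 4 success ranks above a heavier participant at target only if 30/b₄ < 20/b, that is, if b₄ > 1.5 × b, where b₄ and b are their pre-study means.

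- Search over 90 to 240 minutes in steps of 30, with cohorts 1-3 at target and all four of cohort 4 sharing one pre-study mean: the median differed between total cohort 4 success and total failure in 5,634 of 18,018 configurations, by at most 9.7 points. These are counts on a grid, not probabilities.
- Largest case: six heavier participants at 90, four at 180, cohort 4 at 240. The median goes from 87.5% to 77.8%.
- Pre-study durations drawn uniformly from 90-120, 90-180 or 90-240 minutes (20,000 draws each): average drop of 0, 0.3 or 0.9 points.
- After total cohort 4 failure, the four zeros fill the lowest ranks, so the median is the mean of the 3rd and 4th lowest heavier values. With pre-study means of at least 90, it is at least 100 × 70/90 = 77.8%.

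**The case against.** The case for leaving the plan alone has real content.

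- **The table holds more than medians.** It also gives the mean, SD, minimum and maximum, and one cohort 4 failure moves the maximum from 30 to 120 in the illustration. A reader might infer that the whole primary table would look the same whatever cohort 4 does. It would not. This stands. The pooled figures still cannot say which group produced the change.
- **The % reduction median is not fixed.** A reader might extend the result for duration to both endpoints. Individual denominators break it, as step 4 shows, although the shift is small.
- **The SAP took no by-cohort primary table away.** Protocol 9.3.1 mentions per-cohort summaries but refers to 9.3.2 for the primary endpoints, and 9.3.2 already pools them. Table B should not be read as removing a planned primary summary.
- **Cohort 4 is visible elsewhere.** With four participants the listing shows every value. The first secondary endpoint uses weight-specific targets, so total cohort 4 failure with cohorts 1-3 at target would show as 10/14 (71%). This stands: the results are available, though not as a primary summary for that schedule.
- **Pooling has a stated reason.** Small cohorts are a fair argument against four columns, but a weaker one against two. The SAP itself plots a cohort mean for lyso-GL3 (15.3.1.1.1).

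No passage says the pooled median describes the <30 kg schedule. That it might be read that way is a judgement.

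**Conclusion.** The point holds as one about the primary summary, not about concealed data. With full enrolment and at least 8 of 10 heavier participants tolerating 20 minutes, the pooled median shortest duration does not reflect cohort 4 at all. The pooled median % reduction reflects it by at most about 10 points, given pre-study durations of 90-240 minutes and cohorts 1-3 at target. The mean and maximum respond to cohort 4 failures, and the duration Q3 responds if all four fail, but none identifies the group.

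The duration result needs no pre-study figure beyond failing values ranking behind 20 minutes, which is so under the protocol's rule (longer than the maximum observed) and in the SAP if pre-study means exceed the target. It does assume that cohort 4's actual durations are no shorter than those of the heavier participants at target; the tolerance rule sets only an upper limit. The probabilities in step 2 rest on assumed success rates and independence. The change is worth making because it is cheap and bears on the study's own question, but the analysis is descriptive and no test depends on it.

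**What to change.** In SAP 15.1.4, and in the pooling row of Table B:

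- Add two descriptive columns for both primary endpoints: ≥30 kg (cohorts 1-3, 20-minute target, n up to 10) and <30 kg (cohort 4, 30-minute target, n up to 4), the latter limited to n, median, minimum and maximum. Keep the pooled column, as Protocol Table 5 specifies it.
- Order or label the waterfall bars by target group.
- State that any statement about the <30 kg schedule rests on the <30 kg column, not on the pooled median.

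The cost is SAP wording and two columns in the primary tables. It needs no new data and no change to study conduct. The drawback is that the <30 kg column has at most 4 participants and can only be read descriptively.

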15.2 SECONDARY ENDPOINTS

15.2.1 SECONDARY VARIABLES

Data for secondary endpoints at each visit (scheduled and unscheduled) are captured on the Fabrazyme eCRF pages.

15.2.1.1 PROPORTION OF PARTICIPANTS ACHIEVING THE SHORTEST PLANNED DURATION OF INFUSION TIME WITHOUT EXPERIENCING ANY OR THE SECOND IAR

To evaluate the objective the following binary variables will be derived for each participant:

- Whether the participant achieved the shortest planned target duration of infusion (20 minutes for participants ≥30 kg and 30 minutes for participants <30 kg) without experiencing a first (ie, any) IAR (yes/no).
- Whether the participant achieved the shortest planned target duration of infusion time (20 minutes for participants ≥30 kg and 30 minutes for participants <30 kg) without experiencing a second IAR (yes/no).

Document: \\ieedc-

Author:

vnasc01\BIOSdata\Sanofi\Fabrazyme\IAB16602\Biostatistics\Documentation\SAP\SAP\Sanofi\Final

Version Number:

Version\lps17726-16-1-9-sap.docx

Version Date: 22Oct2024

Template No.: CS_TP_BS016 Revision 7 Reference: CS_WI_BS005

Effective Date: 01Nov2021

PROTOCOL LPS17726

Analysis Plan Template

Page 46 of 65

15.2.1.2 PROPORTION OF PARTICIPANTS ACHIEVING INFUSION DURATION SHORTER THAN 90 MINUTES WITHOUT EXPERIENCING ANY OR THE SECOND IAR

To evaluate the objective the following binary variables will be derived for each participant:

- Whether the participant achieved infusion duration shorter than 90 minutes without experiencing a first (ie, any) IAR (yes/no).
- Whether the participant achieved infusion duration shorter than 90 minutes without experiencing a second IAR (yes/no).

A participant will be considered a non-responder ie, "No" if they have an initial planned target duration <90 minutes yet fail to tolerate an infusion during the study treatment period with actual duration <90 minutes. Participants with an initial planned target duration <90 minutes will be considered a responder ie, "Yes" if they tolerate at least one infusion during the study treatment period with actual duration <90 minutes.

15.2.1.3 PROPORTION OF PARTICIPANTS ACHIEVING EACH INFUSION DURATION PLANNED IN THE STUDY WITHOUT EXPERIENCING ANY OR THE SECOND IAR

To evaluate the objective the following binary variables will be derived for each participant:

- Whether the participant tolerated the planned infusion duration without experiencing a first (ie, any) IAR (yes/no), calculated separately per each planned infusion duration.
- Whether the participant tolerated the planned infusion duration without experiencing a second IAR (yes/no), calculated separately per each planned infusion duration.

Document: \\ieedc-

vnasc01\BIOSdata\Sanofi\Fabrazyme\IAB16602\Biostatistics\Documentation\SAP\SAP\Sanofi\Final

Version\lps17726-16-1-9-sap.docx

Author: Version Number: Final V1.0

Version Date: 22Oct2024

Template No.: CS_TP_BS016 Revision 7 Reference: CS_WI_BS005

Effective Date: 01Nov2021

PROTOCOL LPS17726

Analysis Plan Template

Page 47 of 65

